3 STUDY OBJECTIVES

3.1 Primary Objective

The goal of this study is to determine whether 25(OH)D₃ clearance is affected by vitamin D₃ supplementation. The data obtained in this study will be compared to previously obtained “un-supplemented” measurements taken in the same patients. Only subjects who previously participated in the CLEAR or CLEAR-CF protocol and from whom un-supplemented, measurements of 25(OH)D₃ clearance were obtained will be enrolled in this study.

3.2 Secondary Objectives

- To explore whether disease status (chronic kidney disease or cystic fibrosis) modify the 25(OH)D₃ clearance response to vitamin D₃ supplementation.
- To evaluate biomarkers of 25(OH)D₃ clearance during vitamin D₃ supplementation.

4 STUDY DESIGN

This is a single-dose, open-label pharmacokinetic study that uses intravenous administration of a stable deuterium-labeled 25(OH)D₃ to evaluate the metabolic clearance of 25(OH)D₃ in subjects supplementing their diet with a stable dose of vitamin D₃. This study will enroll up to 20 subjects who previously participated in the CLEAR or CLEAR-CF protocol and from whom un-supplemented measurements of 25(OH)D₃ clearance were obtained.

Subjects who qualify and provide written informed consent will be prescribed a stable, standard dose of vitamin D₃ supplement (cholecalciferol, 2000 IU daily by mouth), to be taken throughout the duration of the study (approximately 6 months).

After 3 months of vitamin D₃ run-in, participants will be re-screened for eligibility (prior to receiving the intravenous labeled 25(OH)D₃ study drug). Participants who remain eligible at re-screening will receive a single dose of intravenous labeled 25(OH)D₃. Subsequent blood draws and urine collections will be used to determine the metabolic clearance of 25(OH)D₃ and related parameters. The metabolic clearance of 25(OH)D₃ during stable vitamin D₃ supplementation (obtained from this protocol) will be compared to the metabolic clearance of 25(OH)D₃ in the un-supplemented state (obtained for the same participants during CLEAR or CLEAR-CF) to assess the effects of vitamin D₃ supplementation.

5 CRITERIA FOR EVALUATION

5.1 Primary Efficacy Endpoint

The primary outcome of interest is the metabolic clearance of labeled 25(OH)D₃.

We will measure serum concentrations of 24,25(OH)₂D₃, 25(OH)D₃, 25(OH)D₂, 1,25(OH)₂D₃ and 1,25(OH)₂D₂ at the University of Washington by mass spectrometry. For each participant and time point, a single serum aliquot is used to measure this panel of vitamin D metabolites using by immunoaffinity extraction and HPLC-mass spectrometry (Xevo TQ, Waters Corp., Milford, MA) with deuterated internal standards.⁵³⁻⁵⁶

For each subject, non-compartmental analysis of plasma concentration versus time data will be performed using Phoenix software (Pharsight, Cary, NC). Clearance will be calculated as administered 25(OH)D₃ dose divided by 25(OH)D₃ AUC. We focus on clearance as our primary outcome because it reflects the metabolism of 25(OH)D₃ accounting for circulating 25(OH)D₃ concentration (units of volume/time, akin to creatinine clearance). Clearance is independent of volume of distribution, in contrast to t_{1/2}, which will be evaluated as a secondary outcome. Clearance will be evaluated with and without adjustment for body size.

5.2 Secondary Efficacy Endpoints

- AUC of labeled D₆-25(OH)D₃
- Terminal half-life of labeled D₆-25(OH)D₃

- Volume of distribution in the central compartment of labeled D₆-25(OH)D₃
- Metabolic formation clearance (metabolite/parent AUC ratio) for metabolites of labeled D₆-25(OH)D₃

5.3 Safety Evaluations

An abnormal clinical laboratory value will be documented as an adverse event if one of the following applies:

- The abnormality is not contradicted by a repeat test to confirm the abnormality.
- The abnormality suggests a disease and/or organ toxicity.
- The abnormality is of a degree that requires active management (e.g., requires a medication change, more frequent follow-up, or further diagnostic evaluation).

Change in clinical laboratory findings (if there are specific labs, then why they are appropriate to measure, e.g., BUN or Creatinine for an aminoglycoside)

An adverse event (AE) is any symptom, sign, illness or experience that develops or worsens in severity during the course of the study. Intercurrent illnesses or injuries should be regarded as adverse events. Abnormal results of diagnostic procedures are considered to be adverse events if the abnormality:

- results in study withdrawal
- is associated with a serious adverse event
- is associated with clinical signs or symptoms
- leads to additional treatment or to further diagnostic tests
- is considered by the investigator to be of clinical significance

A serious adverse event is any AE that is:

- fatal
- life-threatening
- requires or prolongs hospital stay
- results in persistent or significant disability or incapacity
- a congenital anomaly or birth defect
- an important medical event

Important medical events are those that do not fit the other definitions of serious adverse events, but the event may jeopardize the patient and may require treatment to prevent one of the listed serious adverse events.

Adverse events will be reported if they occur between the time of informed consent and 30 days after the last study visit. All unresolved adverse events will be followed by the PI until resolution, the adverse event is otherwise explained, or the participant is lost to follow-up. At the last study visit, the investigator will instruct each participant to report any subsequent event that the participant, or participant's personal physician, reasonably believes may be related to the study. The investigator will notify the study sponsor of any death or adverse event occurring after the participant has discontinued participation if the event can be reasonably related to the study.

6 SUBJECT SELECTION

6.1 Study Population

Only participants who successfully completed the CLEAR or CLEAR-CF protocol will be eligible for this study. CLEAR and CLEAR-CF are single-center studies that recruit adults with and without chronic kidney disease (for CLEAR) or with or without cystic fibrosis (for CLEAR-CF) from the University of Washington system and related institutions. CLEAR or CLEAR-CF participants will be approached for participation in this study at the time of their last CLEAR or CLEAR-CF visit, or within 18 months of completing the CLEAR or CLEAR-CF protocol.

6.2 Inclusion Criteria

The main inclusion criterion is the successful completion of related protocol CLEAR or CLEAR-CF, defined as:

- Receipt of D₆-25-hydroxyvitamin D₃ Solution under the CLEAR or CLEAR-CF protocol,
- Completion of at least 7 CLEAR or CLEAR-CF study visits, and
- Absence of adverse events related to D₆-25-hydroxyvitamin D₃ Solution administration during participation in CLEAR or CLEAR-CF

CLEAR and CLEAR-CF enrolled only adults, with additional eligibility criteria related to race, disease status (stage of chronic kidney disease or presence of cystic fibrosis), and screening serum 25(OH)D concentration (10-50 ng/mL).

6.3 Exclusion Criteria

Exclusion criteria will be:

- Inability to give informed consent
- Primary hyperparathyroidism
- Gastric bypass
- Tuberculosis or sarcoidosis
- pregnancy
- Child-Pugh Class B or C cirrhosis (i.e. cirrhosis with ascites, hepatic encephalopathy, bilirubin \geq 2 mg/dL, serum albumin \leq 3.5 g/dL, or PT \geq 4 seconds)
- History of kidney transplantation (unless failed transplant now treated with hemodialysis)
- hemoglobin $<$ 9 mg/dL
- serum calcium $>$ 10.1 mg/dL
- use of active vitamin D receptor agonists (e.g. 1,25(OH)₂D₃ or an analogue, calcitriol) or cinacalcet within 4 weeks
- use of a cytochrome P-450 (CYP) inhibitor or inducer within 4 weeks (table 6.4)
- Unwilling to take vitamin D₃ (cholecalciferol) 2000 IU daily by mouth, as provided by the study

If people do not meet eligibility criteria based on medication use, they will be allowed to participate in the study after an appropriate washout period if their primary physician agrees. For active vitamin D compounds, cinacalcet, and CYP inhibitors and inducers the washout period will be 4 weeks.

Table 6.3. Patient Eligibility – Exclusion criteria
Active vitamin D receptor agonist (e.g. calcitriol) or cinacalcet in last 4 weeks
Child-Pugh Class B or C cirrhosis
Hemoglobin < 9 mg/dl
Serum calcium concentration > 10.1 mg/dl
Pregnancy
Inability to give informed consent
Medications known to strongly induce or suppress the CYP enzymes which metabolize vitamin D (see example list below)

Table 6.4. CYP inhibitors and inducers		
CYP Inhibitors		CYP Inducers
Amprenavir	Imatinib	Avasimibe
Aprepitant	Indinavir	Bosentan
Atazanavir	Itraconazole	Carbamazepine
Casopitant	Ketoconazole	Efavirenz
Cimetidine	Lopinavir	Etravirine
Ciprofloxacin	Nefazodone	Modafinil
Clarithromycin	Nelfinavir	Nafcillin
Conivaptan	Posaconazole	Phenobarbital
Darunavir	Ritonavir	Phenytoin
Diltiazem	Saquinavir	Rifabutin
Dronedarone	Shisandra	Rifampin
Elvitegravir	Telithromycin	St. John's Wort
Erythromycin	Tipranavir	
Fluconazole	Verapamil	
Grapefruit Juice*	Voriconazole	

* Greater than 8 ounces per day

7 CONCURRENT MEDICATIONS

All subjects will be asked to take vitamin D₃ (cholecalciferol) 2000 IU daily by mouth, provided by the study. Vitamin D₃ is a common form of vitamin D supplement that is readily available by prescription or over the counter. Vitamin D₃ is administered orally, and 2000 IU daily is a common dose that is well below the tolerable upper intake level advised by the Institute of Medicine (4000 IU daily). This form and dose of vitamin D supplement is being actively studied in large clinical trials with clinical outcomes, such as the Vitamin D and Omega-3 Trial (VITAL), which will increase the utility of the data generated from this study. Hypercalcemia is a rare but known potentially complication of vitamin D₃ supplementation (more commonly at higher doses), so serum calcium will be checked after 3 months of vitamin D₃ supplementation (at the re-screening visit), prior to administration of the deuterated 25(OH)D₃ study drug. Vitamin D₃ will be obtained from Carlson Laboratories; supporting information is supplied in the protocol appendix. Participants will be allowed to take up to 400 IU daily additional vitamin D supplements (as vitamin D₃ or vitamin D₃, alone or as part of a multivitamin) in addition to

the 2000 IU daily provided by the study. Non-study vitamin D supplements exceeding 400 IU daily will be disallowed.

Other specific allowed and disallowed medications are detailed in Section 6 (Eligibility Criteria). All subjects should be maintained on the same medications throughout the entire study period, as medically feasible, with no introduction of new chronic therapies.

8 STUDY TREATMENTS

8.1 Method of Assigning Subjects to Treatment Groups

All consenting and qualified participants will be assigned to the single treatment arm.

8.2 Blinding

Neither participants nor study investigators will be blinded to the study intervention.

8.3 Formulation of Test and Control Products

We will administer labeled D₆-25(OH)D₃ Solution for Injection, 20 µg/mL intravenously. D₆-25(OH) D₃ Solution for Injection, 20 µg/mL has been manufactured according to current Good Manufacturing Practices by SRI International (Palo Alto, CA).

8.3.1 Formulation of Test Product

The labeled D₆-25(OH)D₃ Solution for Injection, 20 µg/mL prepared by SRI International is formulated in cosolvents to enhance solubility. Each mL contains 20 µg D₆-25(OH) D₃, 60% propylene glycol (60%), 10% ethanol (ETOH) and water (30%) for injection, to volume.

8.3.2 Packaging and Labeling

The formulated drug product has been aliquoted into single-use vials by SRI International and frozen at <60°C for storage. Vial labels include the drug product name, concentration, batch number, manufacture date, and storage conditions, similar to the draft label shown below.

D₆-25-Hydroxyvitamin D₃ Solution for Injection, 20 µg/mL, 5 mL single use vial
 
Subject ID: _____
 
Batch No.: 16504-08 Manuf. Date: Sept 2016
 
Store at ≤ -60°C (-76°F)
 
See protocol for preparation for administration instructions
 
Caution: New Drug -- Limited by Federal (US) law to investigational use. Keep out of the reach of children.
 
Manufactured by SRI International, Menlo Park, CA 94025

8.4 Supply of Study Drug at the Site

Single-use vials will be stored at <60°C at the University of Washington Investigational Drug Services or Kidney Research Institute. Individual doses of D₆-25(OH) D₃ Solution for Injection will be prepared for intravenous administration by the University of Washington Investigational Drug Services by thawing and drawing the appropriate volume into a syringe. The prepared dose of will be calculated according to estimated blood volume based on body weight. The prepared

dosing syringe will be labeled with the participant's full name, date of birth, and medical record number along with the drug contents. Once thawed, the drug product will be infused within eight hours of preparation.

8.4.1 Dosage/Dosage Regimen

Each participant will receive a single intravenous dose of D₆-25(OH) D₃ Solution for Injection, 20 µg/mL. We will use estimated blood volume based on body weight to achieve a target concentration of 5 ng/mL D₆-25(OH) D₃. The target of 5 ng/mL was selected because it will allow precise tracking of circulating deuterated D₆-25(OH) D₃ concentration throughout follow-up (based on known limits of detection for our assay) without substantially perturbing underlying vitamin D status. Theoretically, the dose required to achieve a 5 ng/mL increment in deuterated 25(OH)D₃ concentration can be calculated as the targeted peak concentration multiplied by the volume of distribution, which for 25(OH)D₃ is expected to be equal to blood volume. We will use the formula of Nadler et al (1962) to estimate blood volume for each participant. We will begin the study by administering to each participant a dose of 5 ng/mL x estimated blood volume. A typical dose would be 32 µg (1.6 mL) for an 85 kg individual. We have verified in CLEAR and CLEAR-CF that we achieve target D₆-25(OH) D₃ concentrations with this approach.

8.4.2 Dispensing

All study drug will be dispensed by the University of Washington Investigational Drug Services.

8.4.3 Administration Instructions

The study drug will be administered intravenously on a single occasion over a period of 5 minutes. Subsequent to thawing, the drug product vial may be stored refrigerated (2-8 °C) for up to 24 hours prior to preparation for administration in a syringe. Once prepared for administration and held at room temperature, the solution should be administered within 8 hours.

8.5 Supply of Study Drug at the Site

All single-use vials of formulated D₆-25(OH)D₃ will be shipped overnight on dry ice to the University of Washington Investigational Drug Services, with temperature monitoring. The University of Washington is the sole clinical site for this study.

8.5.1 Storage

Study drug will be securely stored at a temperature <-60°C at the University of Washington Investigational Drug Services or Kidney Research Institute.

8.6 Study Drug Accountability

An accurate and current accounting of the dispensing and return of study drug for each subject will be maintained on an ongoing basis by the University of Washington Investigational Drug Services. The number of study drug dispensed and returned by the subject will be recorded on the Investigational Drug Accountability Record.

8.7 Measures of Treatment Compliance

Each study drug administration will be directly observed by study staff.

9 STUDY PROCEDURES AND GUIDELINES

A Schedule of Events representing the required testing procedures to be performed for the duration of the study is provided in Section 10 (Evaluations by Visit) below and diagrammed in Appendix 1.

Prior to conducting any study-related activities, written informed consent and the Health Insurance Portability and Accountability Act (HIPAA) authorization must be signed and dated by the subject or subject's legal representative. If appropriate, assent must also be obtained prior to conducting any study-related activities.

9.1 Clinical Assessments

9.1.1 Concomitant Medications

All concomitant medication and concurrent therapies will be documented at Screening, Re-screening, Baseline (Study Day 0), and the final Study Visit (Study Visit 10). Dose, route, unit frequency of administration, and indication for administration and dates of medication will be captured.

9.1.2 Demographics

Demographic data will be abstracted from data provided during CLEAR or CLEAR-CF.

9.1.3 Medical History

Relevant medical history, including history of current disease, other pertinent history, and information regarding underlying diseases, will be abstracted from data provided during CLEAR or CLEAR-CF.

9.1.4 Physical Examination

Height and weight will be measured at the Re-screening visit and at Baseline (Study Day 0). When prompted by reports or suspicion of potential adverse effects during follow-up, physical exam findings will be documented by qualified staff (MD, NP, RN, or PA) and will be followed by a physician or other qualified staff immediately or at the next scheduled visit, as indicated.

9.1.5 Vital Signs

Body temperature, blood pressure, pulse and respirations will be measured after resting for 5 minutes at Baseline (Study Day 0), prior to administration of study drug.

9.1.6 Other Clinical Procedures

Physical activity, vitamin D intake, and body composition measured by dual energy X-ray absorptiometry will be abstracted from data provided during CLEAR or CLEAR-CF. Serum and plasma will be collected at Baseline to measure calcium and phosphorus, intact parathyroid hormone, fibroblast growth factor-23, and vitamin D binding protein. Two 24-hour urine collections will be obtained, immediately preceding and following administration of D₆-25(OH)

D₃, to quantify urinary excretion of albumin and the metabolites of deuterated D₆-25(OH) D₃, respectively. Dialysis patients will be exempt from all urine collections.

9.1.7 Adverse Events

Information regarding occurrence of adverse events will be captured throughout the study. Duration (start and stop dates and times), severity/grade, outcome, treatment and relation to study drug will be recorded on the case report form (CRF).

9.2 Clinical Laboratory Measurements

9.2.1 Hematology

A complete blood count will be obtained at the Re-screening Visit.

9.2.2 Blood Chemistry Profile

Serum sodium, potassium, chloride, bicarbonate, random glucose, BUN, creatinine, aspartate aminotransferase (AST/SGOT), alanine aminotransferase (ALT/SGPT), albumin, calcium, and phosphorous will be obtained at the Re-screening Visit.

Repeat serum sodium, potassium, chloride, bicarbonate, random glucose, BUN, creatinine, aspartate aminotransferase (AST/SGOT), alanine aminotransferase (ALT/SGPT), albumin, calcium, and phosphorous will be obtained at Baseline and Study Day 7.

Intact parathyroid hormone (PTH) will be measured at Visits 2 and 5 (Day 0 and 7 gauged from administration of deuterated 25(OH)D₃).

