10 EVALUATIONS BY VISIT

10.1 Screening Visit (Study Visit 0)

The following activities will occur during the screening visit:

- Collect signed consent form
- Confirm successful completion of CLEAR or CLEAR-CF protocol
- Perform focused medical history restricted to study eligibility criteria
- Complete medication inventory through EMR and patient report
- Participants who meet eligibility criteria at the screening visit will be prescribed vitamin D₃, 2000 IU daily by mouth

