10.2 Re-screening Visit (Study Visit 1)

The Re-screening Visit will take place approximately 90 days after the Screening Visit (allowable range 60-180 days). The following activities will occur during the re-screening visit:

- Confirm adherence ($\geq 80\%$) to study vitamin D₃ (by self-report and pill count)
- Repeat focused medical history restricted to study eligibility criteria
- Complete medication inventory through EMR and patient report.
- Physical Exam (height and weight), and Vital Signs (blood pressure, heart rate)
- Collect non-fasting blood sample for measurement of complete blood count and total 25(OH)D.
- Collect non-fasting blood sample for serum sodium, potassium, chloride, bicarbonate, random glucose, BUN, creatinine, AST/SGOT, ALT/SGPT, albumin, calcium, and phosphorous.
- Participants who continue to meet eligibility criteria, at the screening visit and who are adherent ($\geq 80\%$) to study vitamin D₃, will be invited to return for the remaining study visits.
- Provide selected subjects with supplies required for first 24-hour urine collection

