14 STATISTICAL METHODS AND CONSIDERATIONS

14.1 Data Sets Analyzed

All participants who receive the study drug (D₆-25(OH) D₃ Solution for Injection) will be included in the safety analysis.

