APPENDIX 1. SCHEDULE OF STUDY PROCEDURES

Procedure	VISIT 0 SCREENING	VISIT 1 RE-SCREENING	VISIT 2 BASELINE (DAY 0)	VISIT 3 DAY 1	VISIT 4 DAY 4	VISIT 5 DAY 7	VISIT 6 DAY 14	VISIT 7 DAY 21	VISIT 8 DAY 28	VISIT 9 DAY 42	VISIT 10 DAY 56
Informed Consent	X	X									
Focused Medical History	X	X									
Physical Exam and Vital Signs		X	X								
Medications Inventory	X	X	X								X
Blood Samples*		X	X	X	X	X	X	X	X	X	X
24-hour urine collections			X	X							
DNA collection			X								
Prescribe vitamin D ₃	X										
Study Drug Administration			X								

*Blood Draws Detailed in Appendix 2.

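### Study vitamin D3 starts 60-180 days before the first scheduled calcium, and anyone stopped by that calcium falls outside the safety analysis set

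*Combined protocol and SAP*

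**What the plan says.** **Start of the supplement.** Section 10.1 (Visit 0): "Participants who meet eligibility criteria at the screening visit will be prescribed vitamin" D3. Section 4 ties the prescription to eligibility in the same way: "Subjects who qualify and provide written informed consent will be prescribed a stable, standard dose of vitamin" D3.

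**Laboratory criteria.** Table 6.3 lists "Serum calcium concentration > 10.1 mg/dl" as an exclusion. Low hemoglobin (below 9 g/dL in the Synopsis) is another.

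**First measurement.** On chemistry, Section 9.2.2 says "albumin, calcium, and phosphorous will be obtained at the Re-screening Visit", with repeats at Baseline and Day 7. Section 9.2.1 puts the blood count at Re-screening too. Section 10.2 times that visit "approximately 90 days after the Screening Visit (allowable range 60-180 days".

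**Stated purpose.** Section 7 calls hypercalcemia a rare but known complication of vitamin D3. For that reason it has calcium checked after 3 months of supplement, before the tracer.

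**Analysis set.** Section 14.1 defines one set, for safety: "All participants who receive the study drug", which it identifies as the D6-25(OH)D3 injection.

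**The concern.** Two laboratory criteria belong to a list that people must satisfy before they are given vitamin D3, yet the information needed to apply them does not exist in the study until two to six months afterwards.

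Two things are at stake, both about safety reporting.

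- A calcium above 10.1 mg/dL at Visit 1 has no pre-supplement value to stand against, so it cannot be read as caused by the supplement or as already there. Section 2.1 undertakes to change the protocol if hypercalcemia is seen, and that decision needs to know which of the two it is.
- The person stopped by this check never receives the tracer. The complication that Section 7 names as the reason for the check is thus removed from the safety denominator by the check itself.

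**Working it through.** The plan states no figure to reproduce here. The check sets the schedule against the criteria and the analysis set.

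**Step 1. What Visit 0 contains.** Section 10.1 lists consent, confirmation that CLEAR or CLEAR-CF was completed, a focused history, a medication inventory and the prescription. In Appendix 1 the "Blood Samples" row has no mark under Visit 0. Appendix 2 begins at Visit 1.

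**Step 2. Whether an earlier value may stand in.** Sections 9.1.2, 9.1.3 and 9.1.6 say what is abstracted from CLEAR or CLEAR-CF: demographics, medical history, physical activity, vitamin D intake and body composition. Calcium and hemoglobin are not named. Section 10.1 mentions the electronic record only for medications. Under Section 6.1 a person may be approached at the last CLEAR or CLEAR-CF visit or up to 18 months after completion, so an earlier value could be current or long out of date. When calcium was measured in those studies is not in these documents.

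**Step 3. Scheduled calciums against the supplement.**

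| Time point | Days after Visit 0 | Before supplement? |
|---|---|---|
| Visit 1 | 60-180 | No |
| Visit 2 (Day 0) | at least 90 (Section 10.3) | No |
| Visit 5 (Day 7) | 7 days after Visit 2, within one day | No |

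That is 0 of 3. The Synopsis endpoint for change in calcium runs from baseline to 7 days after the tracer, so it does not cover the run-in either.

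**Step 4. Study vitamin D3 taken before the first calcium, at full adherence.** Dose = 2000 IU × days:

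- 60 days: 2000 × 60 = 120,000 IU
- 90 days: 2000 × 90 = 180,000 IU
- 180 days: 2000 × 180 = 360,000 IU

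**Step 5. What happens to a person above 10.1 mg/dL at Visit 1.** Section 10.2 carries forward only "Participants who continue to meet eligibility criteria, at the screening visit and who are adherent". The excluded person gets no tracer, so is outside the Section 14.1 set and has no clearance for the paired test in Section 14.3.

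**Step 6. How often this might arise.** The documents give no rate. As an assumption only, let a proportion p of 20 starters exceed 10.1 mg/dL at Visit 1. The chance of at least one is 1 − (1 − p)^20:

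| p | Chance of at least one in 20 |
|---|---|
| 1% | 18% |
| 2% | 33% |
| 5% | 64% |
| 10% | 88% |

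At any of these rates, people stopped at Visit 1 contribute nothing to the safety set as defined.

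**Step 7. Cost of one draw at Visit 0.** From Appendix 2, chemistry takes 4 mL and the blood count 3 mL, against a total of 143 mL. 4/143 = 2.8%; (4 + 3)/143 = 4.9%.

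**The case against.** The best defense is that the laboratory criteria were always meant as a gate before the tracer. Section 7 states the 3-month timing openly. Section 4 places re-screening ahead of the injection. The Synopsis treats vitamin D3 as a concomitant medication, counts prohibited drugs from 4 weeks before the tracer, and Section 9.2.3 times the pregnancy test to Baseline or the week before dosing. This reading is plausible, and the check does protect people from receiving the tracer while hypercalcemic. But no section states it. Sections 4 and 10.1 make eligibility a condition of the prescription, and Section 10.2 speaks of people who continue to meet the criteria. If the sponsor intends the narrower gate, one clause would say so, but the safety-set gap would remain.

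Visit 0 also has some protection: a focused history, and exclusions for primary hyperparathyroidism, tuberculosis and sarcoidosis. That stands. So does the point that a raised calcium stops the tracer whatever its origin.

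A reader might infer that a person stopped at Visit 1 disappears from the study record. The documents do not support that. Adverse events are reported from consent (Section 5.3), abnormal laboratory values can be documented as adverse events (Section 11.3), and Section 14.2 summarizes calcium at re-screening without restricting this to tracer recipients. Two limits remain. Section 14.2 does not name its population, and Table 11.2 grades relationship only to the study drug, which a person stopped at Visit 1 has not received.

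A reader might also call this a protocol violation under Section 13. Someone measured when the schedule says, and stopped then, has followed the protocol and is a re-screen failure. Finally, one could use the tracer kinetics to argue that any calcium rise is complete before the first test. Those kinetics describe 25(OH)D3, not calcium, and the point does not use them.

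**Conclusion.** The point holds as a modest, inexpensive improvement to safety reporting. As written, the calcium and hemoglobin exclusions cannot screen people before the supplement. No study calcium precedes it, and the first comes after 120,000 to 360,000 IU at full adherence. A person stopped at Visit 1 for calcium above 10.1 mg/dL is outside the one defined safety set, though not outside adverse event recording.

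This rests on the visit schedule as written and on the absence of any provision for a CLEAR, CLEAR-CF or chart calcium. A recent value may exist for some participants; the plan simply does not call for it. No frequency of hypercalcemia is claimed. Absolute risk is low: the dose is half the 4000 IU daily upper level cited in Section 7, which describes the complication as rare. The primary endpoint, its paired analysis and the power calculation are unaffected.

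**What to change.** 1. In Section 14.1, add a second safety set of everyone who takes at least one dose of study-supplied vitamin D3. Report in it the adverse events and the number stopped at Visit 1 for calcium above 10.1 mg/dL. Keep the tracer set for events after the injection.
2. In Sections 6.3, 9.2.1, 9.2.2 and 10.1, require a dated calcium and hemoglobin before prescribing, taken from CLEAR, CLEAR-CF or the medical record within a stated window (90 days is my suggestion). Draw blood at Visit 0 only if no such value exists, and mark this in Appendices 1 and 2.
3. Keep the Visit 1 gate, and report the calcium change from the pre-supplement value to Visit 1.
4. If the laboratory criteria are meant to apply only from Visit 1, say so in Sections 6.3 and 10.1, and still make change 1.

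Change 1 is text only. Change 2 costs no blood where a recent record exists. Otherwise it costs one venipuncture of 4 mL for chemistry, or 7 mL with the blood count. Under Section 16.1 the amendment needs FDA submission and written IRB approval.
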